1. PROTOCOL SUMMARY

1.1. Synopsis

Name of Regulatory Sponsor: Global Coalition for Adaptive Research, Inc (GCAR)	
Name of Funding Sponsor: Operational Medical Systems (OPMED)	
Name of Study Intervention: Multiple interventions will be tested in this adaptive platform trial, and each will be described in intervention-specific cohort appendices to the master protocol	
Name of Active Ingredient: Active ingredients will be described in the cohort appendices.	
Protocol Number: S-21-02	
Full Title of Study: A Phase 2, Multi-center, Multi-arm, Randomized, Placebo-Controlled, Double-Blind, Adaptive Platform Study to Evaluate the Safety, Tolerability, and Efficacy of Potential Therapeutic Interventions in Active-Duty Service Members, Veterans, and Non-Veteran Civilians with Posttraumatic Stress Disorder (PTSD)	
Study Short Title: M-PACT (formerly DOD PTSD APT)	
Study Sites: Approximately 20 sites in the US. A site list is maintained in the eTMF and updated as sites are added. The list is available upon request.	
Studied Period (years): First participant enrolled: Nov 2023 Estimated date last participant completed: Oct 2029	Phase of Development: Phase 2
Duration of Participant Participation: This study consists of a 30-day Screening Period, a 12-week Treatment Period, and a 4-week Safety Follow-up. The total duration of participant participation in this study is up to 20 weeks; if a participant is re-randomized, their total duration of participation will continue for an additional 16 to 20 weeks each time they are re-randomized.	
Objectives: Primary: 
 Determine the efficacy and safety of each intervention for the treatment of PTSD in active-duty service members, veterans, and non-veteran civilians over 12 weeks. Secondary: 
 Evaluate the effect of each intervention on PTSD symptoms, sleep, depression, anxiety, substance use, functional status, mood, cognition, and QOL in active-duty service members, veterans, and non-veteran civilians with PTSD over 12 weeks. 	

- Identify PTSD subtypes through characterization of candidate biomarkers within the following categories:
 - diagnostic subtype biomarkers of population heterogeneity
 - predictive, monitoring biomarkers of treatment response for specific interventions
 - pharmacodynamic biomarkers of intervention effects

Exploratory:

- To explore the utility of physiological, biological, cognitive, and digital measures as diagnostic (e.g., to identify PTSD subtypes), predictive, monitoring, and pharmacodynamic biomarkers in active-duty service members, veterans, and non-veteran civilians with PTSD for use in the design of biomarker extensions and intervention selection.
- To evaluate the effect of each intervention on each PTSD symptom and groups of PTSD symptoms (e.g., cluster scores) in active-duty service members, veterans, and non-veteran civilians with PTSD over 12 weeks.
- To evaluate the effect of each intervention on the relationship between global impression of severity of PTSD and a change in PTSD symptom severity.
- To evaluate the effect of each intervention on participants' most bothersome symptom.
- To evaluate the effect of each intervention on weekly PTSD symptoms, as measured by the PCL-5, Past Week.

Endpoints:

Primary:

Efficacy

- Absolute change from Baseline in CAPS-5-R, Past Month total score at Week 12.

Safety

- Frequency and severity of TEAEs/SAEs.
- Absolute change from Baseline, and new clinically significant findings in clinical laboratory parameters, vital signs, physical examination, ECG.
- Incidence of new or worsening suicidal thoughts or behaviors as measured by C-SSRS.

Secondary:

- Relative change from Baseline to 12 weeks in CAPS-5-R, Past Month total score.
- Response rate: $\geq 30\%$ reduction from Baseline to 12 Weeks in CAPS-5-R, Past Month total score.
- Response rate: $\geq 50\%$ reduction from Baseline to 12 Weeks in CAPS-5-R, Past Month total score.
- Response rate: Achieving remission, defined as CAPS-5-R, Past Month total score < 18 .
- Relative and absolute change from Baseline in CAPS-5-R, Past Month total score at Weeks 4 and 8.
- Absolute change from Baseline at each post-Baseline Visit in:

- PCL-5, Past Week total score (at Weeks 4, 8, and 12)
- PSQI-A
- ISI
- BDI-II
- GAD-7
- TLFB for substance use
- FTND
- B-IPF
- WHOQOL-BREF
- PSS
- BPI
- IDSIQ (mean average IDSIQ scores for 7-days prior to Weeks 4, 8, and 12)
- Diagnostic subtype: Analyses of biomarker levels across all interventions.
- Predictive: Relationship between baseline biomarker levels and absolute change from Baseline in CAPS-5-R, Past Month total score at Week 12 across all interventions or specific interventions.
- Monitoring: Relationship between a change in biomarker levels and absolute change from Baseline in CAPS-5-R, Past Month total score at Week 12 across all interventions or specific interventions.
- Pharmacodynamic: Relationship between a change in biomarker levels with administered doses of specific interventions through Week 12.

Exploratory:

- Modeling of individual or combinations of markers across all time points.
- Absolute change from Baseline to Week 12 in CAPS-5-R, Past Month severity scores on each PTSD symptom and groups of PTSD symptoms (e.g., cluster scores).
- Absolute change from Baseline at each post-Baseline Visit in:
 - CGI-S
 - PGI-S
 - PCL-5, Past Week
- Change from Baseline in the qualitative interview score at Week 12.

Trial Description:

The general structure of the M-PACT consists of a 30-day Screening Period, a 12-week Treatment Period, and a 4-week Safety Follow-up. The trial will include up to 5 open cohorts (it is possible for 1 of the cohorts to begin sooner than the others, as necessary). Importantly, the integration of multi-modal biomarker assessments within the M-PACT allows for defining future cohorts based on to-be-determined biomarker signatures in a multi-stage approach. Initial testing in

non-biomarker-defined cohorts will be referred to as “main stage” testing, while testing in biomarker-defined cohorts will occur within “biomarker extensions.”

In this study, cohorts will be allowed to enter and exit the overall adaptive platform trial, with exit based on a prescribed decision algorithm evaluating data as it accrues, and entry based on the PdM’s decision informed by the DSWG and APEC’s evaluation of potential new interventions for the trial. Thus, non-effective treatments may be identified more rapidly than in a traditional single intervention trial, and the resulting savings can be reinvested in exploring additional potential treatments.

Initially designed as up to 5-arms versus control, the adaptive platform trial will continue enrollment until decisions are made to stop all cohorts. Interim analyses will be conducted at approximately quarterly intervals, beginning after at least 40 participants have been randomized and at least 10 participants have completed the End of Study (EOS) visit. At each interim analyses, unblinded data will be reviewed by an independent, firewalled ISAC and a DSMB. The possible cohort-level decisions that could be made by the prespecified adaptive plan include stopping enrollment to a cohort for futility, stopping enrollment to a cohort for anticipated success, or stopping enrollment to a cohort for reaching the maximum sample size. For cohort-specific interventions intending to pursue a labeling claim (which will be clearly stated in the cohort-specific appendix before cohort initiation), early stopping for success will not be considered. New cohorts for investigation can be added at any time. The DSMB may recommend stopping any cohort for safety reasons.

Candidate biomarker data will be retrospectively analyzed after each cohort has completed main stage testing, and cohort testing may be re-initiated for prospective evaluation of the treatment in a participant population enriched (e.g., either only biomarker “positive” or only biomarker “negative” participants would be enrolled) or stratified based on biomarker status. In addition, candidate biomarkers (which may also be characterized or validated externally to the M-PACT) may be used to stratify randomization across cohorts or as a prospective enrichment strategy at the initiation of a cohort. Exploratory biomarker data will be evaluated throughout the trial to identify additional candidate biomarkers for testing within the M-PACT.

Study Description:

This is a Phase 2 randomized, double-blinded, placebo-controlled study that will evaluate multiple potential therapeutic interventions for PTSD utilizing an adaptive platform trial design. Participants are randomized among the multiple available cohorts in the study, and the resulting randomization enables sharing/pooling of control participants, where all study interventions may be compared to a common control (placebo). This master protocol describes the default procedures and analyses for all cohorts; treatment-specific procedures will be described in the cohort appendices and individual cohorts may have additional eligibility requirements or safety and efficacy procedures.

Following Screening consent and Screening procedures, all eligible participants who meet the protocol-defined criteria will be randomly assigned into 1 of the open cohorts at the site level for which the participant is eligible, with equal randomization among cohorts. Randomization will be stratified by sex, active military vs veteran/non-veteran civilian status, and comorbid depression (yes/no). Following cohort-specific consenting, the participant will be randomly assigned (5:3; study intervention:placebo) within the cohort to receive either study intervention or placebo.

The Treatment Period will be 12 weeks, with efficacy, safety, and in-clinic biomarker assessments and procedures conducted at Weeks 1 and 12. Remote efficacy and safety measures will be conducted at Weeks 4 and 8. In addition, digital monitoring data will be collected remotely throughout the

Treatment Period via smartphone and the Empatica EmbracePlus actigraphy device. Participants will return at Week 16 (4 weeks after last dose of study intervention) for Safety Follow-up. Participants who continue to meet inclusion/exclusion criteria for the study will be given the option to be re-randomized to an alternative cohort study intervention or placebo for which they are eligible, if one is available. Participants can be re-randomized as often as they remain eligible for at least 1 cohort in the study and complete the appropriate washout period.

Number of Participants:
 
The minimum sample size enrolled in each cohort is 64 participants (40 participants per active treatment and 24 participants in each placebo arm). The maximum sample size enrolled in each cohort is up to 160 participants (100 participants per active treatment and 60 participants in each placebo arm).


Diagnosis and Main Criteria for Inclusion:
 
 • ≥ 18 and < 65 years of age at Screening. • Meets DSM-5 criteria for PTSD according to CAPS-5-R, Past Month assessment. • Is at least 3 months post index trauma at Screening. • Has a CAPS-5-R, Past Month total score of ≥ 26 at Screening and Baseline. Note: the CAPS-5 scoring grid will be used to score answers and to calculate the total score to determine eligibility. • Participants must be able to read, speak, and understand English sufficiently to complete the CAPS-5-R, which is the primary efficacy endpoint and is administered by trained Centralized Assessors.

Investigational Product
 
Multiple investigational products will be included in this trial. The dose, frequency, and method of delivery will vary depending upon the open cohort to which the participant is assigned.

Reference Therapy, Dosage, and Mode of Administration:
 
A placebo that matches the active treatment visually and in method and frequency of administration but which contains no active ingredient, will be used for each study cohort.

Criteria for Evaluation
 
Safety/Pharmacovigilance:
 
 • C-SSRS • CSFQ • Adverse events • Concomitant medications • Physical examination • Vital signs (temperature, pulse, respiratory rate, and systolic and diastolic blood pressure) • Clinical laboratory assessments (hematology, clinical chemistry, urinalysis, pregnancy test) • 12-lead ECG 
Efficacy/Effectiveness:

- CAPS-5-R, Past Month
- PCL-5, Past Week
- TLFB for substance use
- FTND
- PSQI-A
- IDSIQ
- BDI-II
- GAD-7
- B-IPF
- PSS
- BPI
- WHOQOL-BREF

Biomarker Collections:

- MRI
- Biological samples (blood and hair)
- Psychophysiological testing
- Cognitive battery
- Actigraphy device (Empatica EmbracePlus)

Statistical Methods:

Primary Estimand: The primary estimand is the difference between treatments (intervention - placebo) in mean absolute change from Baseline (final CAPS-5-R, Past Month total score - Baseline CAPS-5-R, Past Month total score) in final total score at Week 12 during the Treatment Period in active-duty service members, veterans, and non-veteran civilians with PTSD, regardless of treatment adherence, treatment change and discontinuation of study intervention for reasons related to study intervention (lack of efficacy/tolerability) or logistical, and use of prohibited medications, and that death would constitute treatment failure, i.e., a composite strategy.

The first interim analysis will occur after at least 40 participants have been randomized and at least 10 participants have completed the EOS visit. Thereafter, recurring interim analyses will be conducted at approximately quarterly intervals. At each interim analysis, the unblinded data will be reviewed by an independent, firewalled ISAC that will produce a report detailing the current status of each cohort. At each interim analysis the following decisions can be made:

1. Stop enrollment to a cohort for futility.
2. Stop enrollment to a cohort for anticipated success (unless the data will be used to support a labeling claim).
3. Stop enrollment to a cohort for reaching the maximum sample size. This may happen between interim analyses, at which point the cohort will be stopped immediately.

4. Add new cohorts to the trial (this may occur at any time). These additional cohorts could be interventions to be investigated in the main stage or interventions that have completed the main stage and are being investigated additionally in a biomarker extension.

[figure not shown]
Success stopping (for cohort-specific interventions not pursuing labeling claims) will be driven by the predictive probability of success at current N. At any interim analysis, complete data will be available on some participants (those enrolled at least 12 weeks prior to the interim) and incomplete data on others (those enrolled in the 12 weeks prior to the interim). To allow for a successful flexible sample size design, a "Goldilocks" strategy will be employed where the probability of success is predicted, with the assumption that upon receipt of endpoint data from incomplete participants, the final success criteria will be met ([Broglia et al 2014](#)). If this probability is high, the cohort may cease enrollment for "anticipated success." Follow-up of all participants will be conducted to their final endpoint and the final analysis will then be conducted. A cohort will cease enrollment for anticipated success if the predictive probability of success is greater than 90%.

Futility stopping will be governed by the predictive probability of success at the maximum sample size, N. The predictive probability that the final efficacy criteria will be met if the cohort goes forward to the maximum sample size will be computed. If this probability is small, it indicates that even with full enrollment to a cohort, the cohort is unlikely to ultimately be successful. A cohort will stop for futility if the predictive probability is less than 10%.

The DSMB may recommend stopping any cohort for safety reasons.

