The M-PACT is a perpetual trial where cohorts can be added, removed, or extended based on accumulating trial data. Biomarker classification used to categorize the sensitivity of treatment response is unknown at the start of the trial, represented by black figures. Participants have equal probability of randomization to any cohort for which they are eligible. They are then randomized 5:3 between study intervention and placebo (see Figure 1). Candidate biomarkers, which may be common to the trial or specific to a cohort, are tracked along with the primary endpoint to identify potential predictors of, or biomarkers associated with, treatment response. Possible outcomes for cohorts are shown above. **A. Cohort graduation:** Cohort reaches maximum sample size. Drug A is superior to placebo in all participants. **B. Biomarker extension:** Validation. After the main stage of the cohort (target sample size reached or futility or success threshold met), Drug B is not superior to placebo in all participants. Candidate Biomarker X is identified as possibly predictive of treatment response. Validation extension establishes that a drug's treatment effect differs over the range of the biomarker (X+ (dark orange) and X- (white) subgroups). **C. Biomarker extension:** Enrichment. Drug C is not superior to placebo in all participants. Candidate Biomarker Y identifies a treatment sensitive subgroup. Enrichment extension determines if Drug C is superior to placebo in the Y+ (dark green) subgroup. **D. Cohort is dropped for futility:** Future probability of success crosses the futility boundary at an interim analysis. **E. Diagnostic subtype biomarker:** Ongoing data collection and analysis of data from all cohorts, or within a cohort, identifies a Biomarker Z as sufficiently promising to be tested as a diagnostic subtyping biomarker for new Drug E with a mechanism of action related to Biomarker Z, or in a treatment that has already completed the main stage of the platform. Biomarker Z could also be identified externally to the trial and be sufficiently validated to bypass the learning stage of the platform.

Figure 3: Randomization and Re-randomization Flow Chart

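### The secondary endpoint labelled Predictive is a marker-outcome association with no placebo comparison, so as worded it cannot separate predictive from prognostic markers

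*Protocol*

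**What the plan says.** All references are to the protocol.

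- **Objective (Section 1.1, secondary objectives).** The biomarker categories include "predictive, monitoring biomarkers of treatment response for specific interventions".
- **Endpoint (Section 1.1, secondary endpoints).** The matching line reads "Predictive: Relationship between baseline biomarker levels and absolute change from Baseline in CAPS-5-R, Past Month total score at Week 12", with the scope "across all interventions or specific interventions".
- **Use (Section 1.1).** An exploratory objective says the biomarker work is "for use in the design of biomarker extensions and intervention selection". The Trial Description adds: "Candidate biomarker data will be retrospectively analyzed after each cohort has completed main stage testing". A cohort may then be re-opened in an enriched population (only marker-positive or only marker-negative participants) or a stratified one.
- **How candidates arise (Section 1.2, Figure 2 legend).** Markers "are tracked along with the primary endpoint to identify potential predictors of, or biomarkers associated with, treatment response".
- **What the extensions are for (same legend).** "Validation extension establishes that a drug's treatment effect differs over the range of the biomarker". In the enrichment case, "Candidate Biomarker Y identifies a treatment sensitive subgroup", and the drug is then compared with placebo among marker-positive participants.
- **Cohort sizes (Section 1.1).** Allocation is 5:3 active to placebo, with 64 to 160 participants per cohort.

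**The concern.** A predictive marker is one over which the drug's effect against placebo varies. A prognostic marker is related to outcome whatever the treatment. An association between the baseline marker and the change score contains both components and cannot divide them.

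The distinction matters here. Every participant must have a CAPS-5-R total of at least 26 at Screening and at Baseline, so some regression to the mean is to be expected in both arms. Natural course and placebo response add to it. A marker correlated with baseline severity, or with a good outlook generally, can therefore correlate with absolute change without any drug effect.

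The objective and both kinds of extension ask about differential drug effect, which the endpoint line does not describe. The Figure 2 legend also runs predictors of response and markers merely associated with it together. If a prognostic marker were taken into an extension that enrols only marker-positive participants, there would be no marker-negative group in that extension to show the mistake.

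**Working it through.** **Inputs from the protocol.** Allocation 5:3; cohort size 64 (minimum) and 160 (maximum).

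**Check of the plan's own figures.** 64 × 5/8 = 40 and 64 × 3/8 = 24; 160 × 5/8 = 100 and 160 × 3/8 = 60. These reproduce the stated arm sizes exactly. The protocol gives no alpha, effect size or power for the biomarker endpoint, so there is no biomarker figure to reproduce.

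**Assumptions that are not in the protocol.** Two-sided 0.05, one marker, Gaussian data, independent participants, and correlation r between marker and change over the range 0.1 to 0.4.

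**Step 1: a purely prognostic marker (same r in both arms).** Three analyses are compared.

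(a) Active arm only. Power ≈ Φ(atanh(r) × √(n − 3) − 1.96). For r = 0.3 and n = 100: 0.3095 × √97 = 3.048, and Φ(3.048 − 1.96) = 0.862.

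(b) Both arms pooled, adjusted for arm, no interaction term. With one covariate, √(n − 3) becomes √(n − 4). For r = 0.3 and n = 160: 0.3095 × √156 = 3.866, and Φ(3.866 − 1.96) = 0.972.

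(c) Marker-by-treatment interaction in a linear model. There is no true interaction, so a valid test rejects at its nominal level. Simulation (4,000 runs per setting) gave 4.6% to 5.2%.

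Chance that the prognostic marker is flagged ((a) by formula, (b) and (c) by simulation):

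| Cohort | r | (a) active arm | (b) pooled | (c) interaction |
|---|---|---|---|---|
| 40 + 24 | 0.1 | 9% | 12% | about 5% |
| 40 + 24 | 0.2 | 23% | 35% | about 5% |
| 40 + 24 | 0.3 | 47% | 67% | about 5% |
| 40 + 24 | 0.4 | 73% | 91% | about 5% |
| 100 + 60 | 0.1 | 17% | 24% | about 5% |
| 100 + 60 | 0.2 | 51% | 72% | about 5% |
| 100 + 60 | 0.3 | 86% | 97% | about 5% |
| 100 + 60 | 0.4 | 99% | 100% | about 5% |

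Adding placebo participants without an interaction term makes the prognostic marker easier to flag. The problem therefore does not depend on how the scope of the endpoint is read.

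**Step 2: a truly predictive marker (r on drug, 0 on placebo).** This shows what the interaction test costs. With a standardised marker, the standard error of the slope difference is about √[(1 − r²)/n_active + 1/n_placebo].

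- r = 0.3, 100 + 60: √(0.91/100 + 1/60) = 0.1605; 0.3/0.1605 = 1.869; Φ(1.869 − 1.96) = 0.46. Simulation: 46%.
- r = 0.3, 40 + 24: √(0.91/40 + 1/24) = 0.2538; 0.3/0.2538 = 1.182; Φ(1.182 − 1.96) = 0.22. Simulation: 21%.

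For r = 0.2 and 0.4 the simulated power is 23% and 70% at 100 + 60, and 11% and 34% at 40 + 24. For the same marker with r = 0.3, the active-arm test rejects in 86% (100 active) and 47% (40 active). Those are the same rates as for the prognostic marker, so that test does not discriminate between the two.

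**The case against.** **Endpoint lines need not state a contrast.** The primary efficacy endpoint does not mention placebo either; its contrast appears only in the primary estimand under Statistical Methods. Model detail belongs in an analysis plan, which is not at hand. This has force for endpoints that are participant-level variables. It has less force here, because this endpoint is itself a relationship: the line already states the quantity to be estimated, and that quantity does not match its label. An analysis plan with an interaction term would estimate something other than what the protocol says.

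**The line is not restricted to treated participants.** A reader might infer a single-arm analysis. The text does not say so; placebo inclusion is unspecified. This stands, and it is why both readings are computed above.

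**The plan has safeguards.** A reader might infer that the plan would send the wrong markers into enrichment extensions. The protocol does not support that: it ties no statistic or threshold from this endpoint to the choice of an extension, the validation extension tests effect modification directly, and the enrichment extension is placebo-controlled. A merely prognostic marker costs efficiency and weakens the case for restricting the population; it does not by itself produce a false claim of efficacy. This stands. The gap that remains is the extension confined to one marker group.

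**The percentages are partly by construction.** The 5% is the nominal level of any valid interaction test, and the 86% and 97% depend on an assumed correlation. This stands; they are illustrations, not properties of the plan.

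**Gating on the interaction would lose real candidates.** With 46% power in a full cohort and 21% in a minimum one at r = 0.3, this is right. It argues against a significance threshold, not against estimating the interaction.

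**Conclusion.** The point holds as a defect in how the endpoint is defined. As worded, the endpoint counts a purely prognostic marker as predictive, contrary to the objective it serves and to the use the extensions make of it.

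The size depends on the marker. For correlations of 0.1 to 0.4 in a full cohort, an analysis without the placebo contrast would flag a prognostic marker in 17% to 99% of cohorts (active arm) or 24% to 100% (pooled), against about 5% with the interaction. The cohort sizes are the protocol's; the alpha, the correlations, the single Gaussian marker and independence are assumed.

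Two stronger readings should be avoided. The endpoint does not find only prognostic markers, since it flags both kinds. Nor is it established that wrong markers will reach an extension, only that they could. This should be corrected, but it does not threaten the primary efficacy comparison.

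**What to change.** 1. Redefine the endpoint, for each intervention, as the active-versus-placebo difference in the relationship between baseline biomarker and absolute change in CAPS-5-R at Week 12 (the biomarker-by-treatment interaction), adjusted for baseline CAPS-5-R. Use the eligible placebo controls that the platform's sharing of controls allows, and state which these are.
2. State that the interaction estimate with its interval is the main evidence when extension candidates are chosen, without requiring significance.
3. If the association without a placebo contrast is kept, describe it as association with outcome, prognostic and predictive components not separated. Calling it prognostic would also be wrong, because an active-arm association mixes the two.

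**Cost.** The change is to one endpoint's wording and its analysis. Placebo participants are already randomised in every cohort, and the Study Description sets out the biomarker assessments without distinction by arm, so no new data collection appears to be needed. The real downside is precision: the interaction will often be estimated with a wide interval, above all in cohorts that stop near the minimum size, and the evidence for any one candidate will look weaker than a plain correlation would suggest. Sharing placebo controls across cohorts would recover some of that precision.
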